## 9.5 Data Analyses

Our primary analysis will use children's original treatment assignment regardless of adherence (intention to treat). We will begin by calculating descriptive statistics for baseline demographics and clinical characteristics by vitamin D treatment groups (600 IU vs 1000 IU vs 2000 IU). Our primary outcome measure of vascular health is brachial artery FMD expressed as a percentage. We will use mixed-effects models with fixed effects of time (baseline, 3 months, and 6 months), the treatment\*time interaction, and random subject effects to test for differential changes in FMD over time and differences in FMD at six months. We are primarily interested in the comparisons of each higher dose (1000 IU and 2000 IU) to the lower dose (600 IU) at six months ( $\alpha=0.025$  for each comparisons). The mixed-effects model will allow unbiased estimation of the treatment effects at six months even if some 6-month data are missing because of the incorporated dependence among baseline, 3-month and 6-month assessments (assuming data are missing at random). We will test the main effect of vitamin D supplementation (three groups) at 3 and 6 months and pairwise comparisons of the groups receiving the larger doses of vitamin D with the group receiving 600 IU. If differences are detected across the 3 groups, we will test for a dose response in FMD across doses by using a linear contrast of coefficients test ( $\alpha=0.05$ ). We will use the same methodology to test the effects of higher doses of vitamin D on pulse-wave velocity, our primary measure of arterial stiffness.

The second part of our primary analysis of our trial is to determine whether higher doses of vitamin D will result in improvements in insulin sensitivity and metabolic syndrome markers over time. We will use mixed-effects models with fixed effects of time (baseline, 3 months, and 6 months), and the treatment time interaction with random subject effects to test for differential changes in secondary outcomes over time. We will test the main effect of treatment (three groups) at 3 and 6 months and pairwise comparisons of the groups receiving the larger doses of vitamin D with the group receiving 600 IU. All tests will be two sided with  $\alpha=0.05$ .

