We will explore the mediating effects of inflammatory markers (hs-CRP, IL-6, TNF- $\alpha$ ) and adipokines (leptin and adiponectin) on the temporal relationship between vitamin D and vascular health. We hypothesize that vitamin D effects on vascular health may be driven by inflammatory processes and adipokines. An analysis that would complement this hypothesis would be a mediation analysis where we demonstrate that the effect of vitamin D on vascular health is partially mediated by our measures of inflammation and adipokines. We propose to use single-mediator and multiple-mediator methods incorporating product of coefficients to test for mediation. For the simple single-mediator analysis, we first must demonstrate that the high dose vitamin D has a significant effect on each mediator (inflammatory markers and adipokines) at three and six months using a general linear model. We will then test whether 6-month vascular health is correlated with each mediator. Both tests would have to be significant for there to be evidence of mediation. We will estimate the mediated effect by taking the product of the following coefficients: 1) the coefficient for the intervention effect on the mediator, and 2) the coefficient for the mediator in a model testing the intervention effect on

vascular health controlling for the potential mediator. This estimate will provide the reduction in the effect of vitamin D on vascular health when adjusted for the mediator. The confidence interval for the mediated effect will be calculated using bootstrap methods. Since our vitamin D intervention is hypothesized to target multiple mechanisms, we will test for a multiple-mediator model after single mediation is thoroughly investigated.

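### The mediation analysis requires two preliminary significance tests, one apparently at both follow-up visits, and gives the planned bootstrap interval no role in the decision, so mediation that builds up by 6 months is likely to be discarded

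*Combined protocol and SAP*

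**What the plan says.** The mediation paragraph of section 9.5 (Data Analyses) serves the secondary objective in section 1.2 and is framed as exploratory: "We will explore the mediating effects of inflammatory markers". It sets out these steps.

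- **Method.** The plan names "single-mediator and multiple-mediator methods incorporating product of coefficients to test for mediation".
- **First test.** The high dose must show a "significant effect on each mediator (inflammatory markers and adipokines) at three and six months using a general linear model".
- **Second test.** "We will then test whether 6-month vascular health is correlated with each mediator". Adjustment for dose is not mentioned, and the visit at which the marker is taken is not given.
- **Condition.** "Both tests would have to be significant for there to be evidence of mediation".
- **Estimate.** The mediated effect is the dose effect on the marker multiplied by a second coefficient, "the coefficient for the mediator in a model testing the intervention effect on" vascular health. That second coefficient is therefore adjusted for dose.
- **Interval.** "The confidence interval for the mediated effect will be calculated using bootstrap methods". The text does not say that the interval must exclude zero, or that it enters the conclusion at all.

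No alpha is given for the two tests. The preceding paragraph, on secondary outcomes, ends "All tests will be two sided with" an alpha of 0.05, and that level is assumed below.

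**The concern.** The only sentence that says what counts as evidence of mediation rests on two preliminary tests, neither of which is a test of the mediated effect. The product of coefficients with its interval addresses that effect directly. It is planned, but has no stated part in the decision.

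The first test causes the main difficulty. The trial's endpoint is at 6 months. A marker change that is modest at 3 months and larger at 6 months can carry an effect on 6-month FMD, yet it fails a condition that needs significance at both visits. A required condition blocks a true finding whether or not further evidence would also be needed.

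The second test has a different weakness. An unadjusted correlation pools the arms, so a dose that moves both marker and FMD creates some correlation even where the marker has no effect on FMD. This matters only if passing the two tests is itself taken as a finding of mediation.

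At stake is the answer to the secondary objective: whether inflammation and adipokines underlie any vascular effect.

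**Working it through.** **Plan's own figures.** The plan gives no power or error rate for the mediation condition. The figures in section 9.2 that supply the inputs do reproduce.

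- FMD%: 1.6 / (2.6 × √(2/56)) = 3.256. Subtracting 2.241 (two-sided alpha 0.025) gives 1.015, so power is 84.5%; the plan states 84%.
- Secondary outcomes: 0.61 × √(56/2) = 3.228. Subtracting 1.960 gives 1.268, so power is 89.8%; the plan states 89%.

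**Inputs from the plan.** 56 evaluable per arm; one higher dose against 600 IU; dose effect on FMD of 1.625/2.6 = 0.625 SD (25% of 6.5%, SD 2.6%).

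**Assumptions not in the documents.** Marker effects of 0.3 to 1.0 SD; marker-to-FMD slope 0.3; correlation of 0.6 between the marker at 3 and 6 months; alpha 0.05.

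**Why the 3-month requirement costs power.** Passing at both visits cannot be more likely than passing at the weaker one. Power for a marker effect d is about Φ(d × √28 − 1.96).

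- d = 0.3: Φ(1.587 − 1.960) = 35%
- d = 0.5: Φ(2.646 − 1.960) = 75%

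With 0.3 SD at 3 months, at most about 35% of true cases can pass, however strong the 6-month effect is.

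**Simulated detection of true mediation.** There were 2,000 to 4,000 trials per scenario. A Monte Carlo distribution of the product stood in for the bootstrap. Ranges are over repeat runs.

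| Marker effect, 3 then 6 months | Two-test condition | 95% interval for product |
|---|---|---|
| 0.3 then 0.5 SD | 30–32% | 67–69% |
| 0.4 then 0.4 SD | 37–40% | 47–50% |
| 0.6 then 0.6 SD | 76–79% | 78–81% |

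In the first row, requiring both the condition and the interval gives 29%. Dropping only the 3-month requirement gives 68–74%. The loss therefore comes from the 3-month requirement.

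**Check with an actual bootstrap** (400 resamples, 2,000 trials, slope 0.4, visit correlation 0.5, 6-month effect 0.61 SD). The condition detects 4%, 33% and 83% for 3-month effects of 0, 0.3 and 0.61 SD. The interval detects 89–90% throughout.

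**No marker effect on FMD.** With equal arms, a dose effect a on the marker and c on FMD induces a correlation of r = 0.25ac / √[(1 + 0.25a²)(1 + 0.25c²)]. With c = 0.625, r is 0.072, 0.105 and 0.133 for a = 0.5, 0.75 and 1.0. Simulated rates:

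| Marker effect (both visits) | Two tests alone | Interval alone | Both required |
|---|---|---|---|
| 0.5 SD | 9–10% | 3.4–3.6% | 1.8% |
| 0.75 SD | 17–19% | 4.8–4.9% | 2.5% |
| 1.0 SD | 29–32% | 5.3–5.7% | 2.6% |

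If dose does not move FMD (c = 0), the two tests alone pass in 3–5% of trials.

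**The case against.** **The two tests are a precondition.** A reader might infer that the plan declares mediation from the two tests in place of the bootstrap interval, and so passes markers that have no effect on FMD. The documents do not support that. The wording is that both tests would have to be significant, which makes them necessary. The same paragraph names the product of coefficients as the means of testing mediation and takes its second coefficient from a model containing dose. If the interval must also exclude zero, the false-positive rate is 2–3%, below that of the interval alone. This objection stands, so the false-positive figures apply only if passing is treated as sufficient, which the text neither states nor excludes.

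**The visits may be meant separately.** Section 9.5 uses similar wording for treatment effects on FMD tested at each of 3 and 6 months. On that reading, with the 6-month marker test used, the loss disappears. This is possible, but the paragraph asks that a significant effect be shown at three and six months, and joint significance is the natural reading. The ambiguity itself needs removing.

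**The late-building profile is assumed.** This is correct: the documents give no marker effect sizes, and with a constant 0.6 SD little or nothing is lost.

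**A 3-month change bears on temporal order.** This is a fair point. It supports reporting the 3-month effect; it does not require making significance there a condition.

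**Conclusion.** The concern holds as a minor point. The plan makes two indirect tests a requirement for evidence of mediation and leaves the direct one, the interval for the product, without a stated role. If significance is needed at both visits, detection of mediation that builds up by 6 months falls from about 67% to about 30% under the assumptions listed. The loss is about 10 points for a constant 0.4 SD effect and small or none for a constant 0.6 SD.

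The false-positive side is conditional. If passing the two tests were taken as sufficient, and dose moved both marker and FMD (FMD by 0.625 SD), about 9–30% of trials would pass for marker effects of 0.5 to 1.0 SD, against about 4–5% for the interval. The excess disappears if the interval must also exclude zero, or if dose does not move FMD.

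The size rests on assumed marker effects, slope, visit correlation and alpha. The primary FMD comparison and the sample size are unaffected.

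**What to change.** In section 9.5, replace the sentence requiring both tests to be significant with a rule to this effect: evidence of mediation is a 95% bootstrap interval for the product of coefficients that excludes zero, with the marker measured at 6 months and its coefficient taken from the model that includes dose.

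Report descriptively the dose effects on each marker at 3 and 6 months, with the 3-month effect as supporting evidence on temporal order, and the correlation of each marker with 6-month vascular health.

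The cost is a change of wording, since the bootstrap is already planned. The downside is that an interval is computed for every marker and dose comparison: five markers × two comparisons = 10 intervals per vascular outcome. These should be labelled exploratory and unadjusted for multiplicity. The interval does not remove confounding between marker and FMD, for example by adiposity, and the report should say so.

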**Design and Outcomes**

In a double-blinded, controlled trial, we propose to randomize 229 eligible children to receive either 600 IU (conventional supplementation, current recommended dietary allowance), or 1000 IU or 2000 IU (enhanced supplementation) of vitamin D3 daily for six months.

The primary outcome measure will be change in brachial flow-mediated dilation percentage at 6 months (FMD%); FMD% is a measure of vascular endothelial function. The secondary outcome measures will include (1) pulse-wave velocity (PWV) – a measure of arterial stiffness, (2) central and systemic blood pressure, (3) fasting blood glucose concentration, (4) 1/fasting insulin concentration as a surrogate for insulin resistivity, (5) lipid profile indices, (6) adipocytokines (plasma leptin, and adiponectin) and systemic markers of inflammation (plasma high-sensitivity CRP, IL-6, TNF- $\alpha$ ).

Eligible participants will be scheduled for enrollment within eight weeks of the initial screening visit. Follow-up visits will occur approximately at three months and six months after enrollment. FMD%, PWV, biochemical measurements, and inflammatory markers will be obtained at each study visit; DXA scan will be done at enrollment and at 6 months.

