### 1.2 Secondary Objectives

To examine whether downregulation of systemic inflammatory markers and adipokines underlie the effects of vitamin D on vasculature and metabolism. We hypothesize that vitamin D effects on vascular health and metabolism may be driven by the attenuation of obesity-associated inflammation.

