## 2. **BACKGROUND AND RATIONALE**

### 2.1 Background on Condition, Disease, or Other Primary Study Focus

Childhood obesity is a major public health problem in the United States (US). In 2007-2008, 32% of 2- to 19-year-old US children were either obese (BMI  $\geq 95^{\text{th}}$  percentile) or overweight (BMI 85th - 94th percentile). Obese and overweight children exhibit cardiovascular disease (CVD) risk factors and have a high risk of metabolic syndrome (i.e. large waist circumference, hypertension, fasting hyperglycemia, hypertriglyceridemia, and low levels of high-density lipoprotein (HDL) cholesterol). Obesity and its atherogenic risks track from childhood to adulthood, increasing the risk of adult CVD and pointing to the need for developing primary prevention strategies in affected children.

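### The mediation model names only arm and marker, so adiposity acting on both marker and FMD% can pass for mediation, and the bootstrap interval does not correct this

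*Combined protocol and SAP*

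**What the plan says.** The mediation part of Section 9.5 covers hs-CRP, IL-6, TNF-α, leptin and adiponectin. It has four steps.

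1. A general linear model must show an arm effect on the marker at three and six months.
2. "We will then test whether 6-month vascular health is correlated with each mediator". Steps 1 and 2 must both be significant before mediation is claimed.
3. The mediated effect is the product of the arm-to-marker coefficient and "the coefficient for the mediator in a model testing the intervention effect on" vascular health, with the marker as the only stated control variable. The plan interprets the product as follows: "This estimate will provide the reduction in the effect of vitamin D on vascular health when adjusted for the mediator". It adds: "The confidence interval for the mediated effect will be calculated using bootstrap methods".
4. Because several mechanisms are expected, "we will test for a multiple-mediator model after single mediation is thoroughly investigated".

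No covariate is named for either regression, and none is ruled out. None carries over from the mixed models earlier in Section 9.5, which list only time, treatment by time and random subject effects. The sensitivity analyses under Missing Data deal with missing values only. No assumption about marker-outcome confounding is stated.

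**The concern.** Children are randomised to a dose, not to a marker level. The arm-to-marker coefficient is therefore protected and the marker-to-FMD coefficient is not. Anything that drives both marker and FMD% enters the second coefficient and is then multiplied into the mediated effect.

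The protocol points to a likely shared cause. Section 1.2 proposes that vitamin D effects "may be driven by the attenuation of obesity-associated inflammation", and Section 2.1 says: "Obese and overweight children exhibit cardiovascular disease (CVD) risk factors". The bootstrap resamples the same regression, so it captures sampling spread and leaves the bias in place.

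At stake is the answer to the secondary objective in Section 1.2, whether inflammation and adipokines explain any vitamin D effect. Part of a reported mediated effect could be ordinary adiposity-related correlation.

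**Working it through.** **Inputs from the documents (Section 9.2).** 56 completers per arm, FMD% SD 2.6, target difference 1.6 points, and a standardised effect of 0.61 quoted for the secondary outcomes.

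**Design figure reproduced.** 1.6 / (2.6 × √(2/56)) = 3.26. Less the two-sided 0.025 critical value 2.24, this leaves 1.01, so power is 84.5% (83.6% with the t distribution). The plan states 84%.

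**Assumed, because the documents are silent.** Dose effect on the marker: 0, 0.15, 0.3 or 0.61 SD. Adiposity-induced marker-FMD correlation r: 0 to 0.3. Visit-to-visit correlation: 0.6 for the marker, 0.5 for FMD%. Direction as hypothesised: vitamin D lowers the marker, adiposity raises the marker and lowers FMD%.

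**Algebra.** If adiposity loads √r on marker and on FMD%, the marker coefficient in the arm-plus-marker model is off by about r (in SD units).

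False product = (dose effect on marker) × r × 2.6.

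At 0.3 SD:
- r = 0.1: 0.3 × 0.1 × 2.6 = 0.08 points, 5% of 1.6
- r = 0.2: 0.16 points, 10%
- r = 0.3: 0.23 points, 15%

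**The bootstrap does not help.** A single-visit simulation used a 0.61 SD dose effect, no true mediation and loadings of 0.3, 0.5 and 0.6 (r = 0.09, 0.25, 0.36). The marker coefficient averaged 0.085, 0.251 and 0.365 in magnitude when the truth was 0. The nominal 95% interval covered zero in 85.4%, 31.7% and 12.7% of trials. With the shared cause in both models, the coefficient returned to about 0 and the interval excluded zero in 5.7%, 8.7% and 5.9%.

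**The written procedure.** 2,000 simulated trials per cell, 500 resamples, one higher dose against 600 IU, α = 0.05, direct effect on FMD% 0.61 SD, no true mediation. Mediation is declared when the arm-to-marker test is significant at both visits, the plain 6-month correlation is significant, and the bootstrap interval excludes zero. The adjusted version keeps the two-test requirement, applied to adjusted coefficients, and assumes that baseline DXA fat captures the shared cause.

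| Dose effect on marker | Plan, r = 0 | r = 0.1 | r = 0.2 | r = 0.3 | Adjusted, r = 0 to 0.3 |
|---|---|---|---|---|---|
| 0 | 0.0% | 0.1% | 0.4% | 1.1% | 0.1% |
| 0.15 SD | 0.1% | 0.9% | 2.3% | 4.1% | 0.1–0.3% |
| 0.3 SD | 0.5% | 3.4% | 11.7% | 18.1% | 0.9–1.2% |
| 0.61 SD | 2.9% | 14.3% | 45.9% | 73.2% | 4.1–5.1% |

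With no direct effect, the plan's rates are similar: 0.6, 3.2, 9.6 and 17.9% at 0.3 SD, and 3.0, 10.8, 39.5 and 72.1% at 0.61 SD.

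**When mediation is real.** With a true coefficient of 0.2 SD FMD% per SD of marker and r = 0.2, a 0.3 SD dose effect gives a true product of 0.3 × 0.2 × 2.6 = 0.16. The written model returned 0.32 and the adjusted model 0.15. At 0.61 SD the figures are 0.32 true, 0.64 written and 0.32 adjusted. At r = 0.1 and 0.3 SD the expected written value is 0.3 × 0.3 × 2.6 = 0.23, half as large again as the truth.

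**Multiple mediators.** With five markers sharing only adiposity, each coefficient's bias falls to r / (1 + 4r). At r = 0.2 this is 0.2 / 1.8 = 0.11. With equal dose effects on all five, the total bias is 5 × 0.11 = 0.56, against 0.20 for one marker. At 0.3 SD on every marker (an upper scenario), the interval for the total product excludes zero in 15.5% and 39.8% of trials at r = 0.1 and 0.2, against 2.0% and 2.5% with baseline adjustment.

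**The case against.** The case for leaving the plan alone has real parts.

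- **The plan is silent rather than wrong.** A general linear model can hold covariates, and none is excluded. That stands. But the text defines the second coefficient by arm and marker, and the preceding step is a plain correlation. An analyst who follows it literally gets the confounded estimate, and one who does not must choose covariates after the fact.
- **The stakes are low.** The analysis is labelled exploratory and no primary or safety conclusion depends on it. That stands and limits the weight of the point.
- **The large percentages need strong assumptions.** Values of r from 0.2 to 0.3 require adiposity correlations of about 0.45 to 0.55 with both marker and FMD%, in a cohort already restricted to the 85th BMI percentile and above. The 0.61 SD figure is an effect size used for a power statement, not an expected marker effect. At r = 0.1 and 0.3 SD or less, false mediation stays below 5%, because the two-test requirement screens out much of it. That stands for the false-positive rate. The bias in the estimate remains.
- **Direction matters.** If the dose effect on the marker runs opposite to the hypothesis, the plan's rates at 0.3 SD fall to about 4% and 12% at r = 0.2 and 0.3.
- **Adjustment removes only measured confounding.** If the shared cause is wholly unmeasured, the adjusted version with both tests kept still declares false mediation in 2.0% and 4.6% of trials at 0.3 SD (r = 0.2 and 0.3), and in 7.9% and 14.3% at 0.61 SD. That stands, but these are well below the plan's rates.

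**Conclusion.** The concern holds. As written, the marker-to-FMD coefficient is not randomised, has no stated adjustment, and is biased by roughly the correlation that a shared cause induces. Neither the bootstrap interval nor the multiple-mediator model removes this. The two-test requirement is not the source of the bias.

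The mechanism is certain; the size is not. Systematic false mediation needs a real dose effect on the marker, which is also the case in which mediation would be reported. For a modest dose effect of 0.3 SD, the spurious mediated effect is 0.08 to 0.23 FMD% points, and false mediation is declared in about 3% to 18% of trials for r from 0.1 to 0.3. The rates of 40% or more in the single-marker analysis need both upper assumptions together. The point bears only on the exploratory answer to the secondary objective. It is minor to moderate, and worth correcting because the correction is cheap.

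**What to change.** In the mediation part of Section 9.5:

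1. Fit both the marker and the outcome regressions with arm, baseline marker, baseline FMD% and baseline DXA percent fat, in the single- and multiple-mediator models. Use baseline rather than 6-month adiposity, because the latter is post-randomisation.
2. Replace the plain 6-month correlation with the marker coefficient from the adjusted outcome model. The two-test requirement can stay, applied to the adjusted coefficients.
3. Base the conclusion on the bootstrap interval for the adjusted product.
4. State the assumption of no unmeasured marker-outcome confounding.

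**Cost.** Plan wording and a little more analysis. No new data are needed. FMD% and the biochemical measures are scheduled at enrolment, and the Design and Outcomes summary says: "inflammatory markers will be obtained at each study visit; DXA scan will be done at enrollment and at 6 months".

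Power for true mediation without confounding changes little. With a true coefficient of 0.2 it goes from 11% to 13% at a 0.3 SD dose effect and from 47% to 44% at 0.61 SD. With 0.3 it goes from 17% to 22% and from 72% to 73%.

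If there is no confounding at all, the adjusted version gives slightly more false positives than the plan: 0.9% against 0.5% at 0.3 SD, and 4.3% against 2.9% at 0.61 SD. Dropping the two-test requirement would raise the adjusted rates further, to 2.3–2.8% and 5.3–6.6% across r = 0 to 0.3.
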